8.6. Solicited adverse events

Solicited local and general AEs will be collected among RTS,S vaccinated groups in the first 50 subjects enrolled in Groups 1 and 2 and all subjects enrolled in group 3 (Reactogenicity Cohort) for seven days (day of vaccination and six subsequent days) after each dose of vaccine. On the day of vaccination for each vaccine dose, the evaluation will be carried out by the study clinician at the KCRC. Seven days after each vaccination a field worker will visit each subject and review the memory aid for solicited local and systemic AEs and unsolicited AEs that have occurred since vaccination and per protocol scheduled anti-malarial treatment, if applicable.

Local (injection site) adverse events

- Pain at injection site
- Swelling at injection site

Systemic adverse events

- Fever (temperature $\geq 37.5^{\circ}\text{C}$)
- Headache
- Gastrointestinal problems
- Fatigue
- Muscle ache

The visiting field worker will record these adverse events during the field worker visits.

8.6.1. Assessment of intensity

Table 8. Intensity Scales for Solicited Symptoms in Adults

Pain at injection site	0	Absent
	1	Painful on touch
	2	Painful when limb is moved
	3	Pain that prevents normal activity
Swelling at injection site	0	Absent
	1	Present and is easily tolerated
	2	Present and interferes with normal activity
	3	Present and prevents normal activity
Fever	0	$<37.5^{\circ}\text{C}$ (99.5°F)
	1	37.5°C (99.5°F) to 38.0°C (100.4°F)
	2	$>38.0^{\circ}\text{C}$ ($>100.4^{\circ}\text{F}$) to 39.0°C (102.1°F)
	3	$>39.0^{\circ}\text{C}$ (102.1°F)
Headache	0	Normal
	1	Headache feeling is easily tolerated
	2	Headache feeling interferes with normal activity
	3	Headache feeling prevents normal activity
	0	Gastrointestinal symptoms normal
	1	Gastrointestinal symptoms that are easily tolerated

Gastrointestinal symptoms (nausea, vomiting, diarrhea)	2	Gastrointestinal symptoms that interfere with normal activity
	3	Gastrointestinal symptoms that prevent normal activity
Fatigue	0	Normal
	1	Fatigue that is easily tolerated
	2	Fatigue that interferes with normal activity
	3	Fatigue that prevents normal activity
Muscle ache	0	Absent
	1	Muscle ache that is easily tolerated
	2	Muscle ache that interferes with normal activity
	3	Muscle ache that prevents normal activity

8.6.2. Assessment of causality

The investigator is obligated to assess the relationship between investigational product and the occurrence of each solicited AE/SAE. The investigator will use clinical judgment to determine the relationship. Alternative causes, such as natural history of the underlying diseases, concomitant therapy, other risk factors and the temporal relationship of the event to the investigational product will be considered and investigated. The investigator may also consult the Investigator Brochure and/or Product Information, for marketed products, in the determination of his/her assessment. The investigator may change his/her opinion of causality in light of follow-up information.

All solicited local (injection site) reactions will be considered causally related to vaccination.

Relatedness to the study product of all other solicited AE/SAEs will be classified by the same criteria established in 8.2.2.

8.6.3. Follow-up and management of adverse events

Follow-up of Solicited AEs/SAEs will be in accordance with section 8.3. AE/SAEs will be managed by the clinical team at KCRC, if possible, until resolution or study completion with nursing and clinical staff providing care under the supervision of the PI. Anything that requires treatment beyond what the KCRC can manage will be referred to an appropriate medical facility, but the staff will continue to follow-up as per section 8.3. At the end of the study, the KCRC staff will refer all subjects with unresolved/chronic AE/SAEs to an appropriate provider for continued management, but will continue to follow-up and document the AE/SAEs as appropriate per section 8.3.

9. CLINICAL MONITORING

Site monitoring is conducted to ensure that the rights and well-being of human subjects are protected, that the reported trial data are accurate, complete, and verifiable, and that the conduct of the trial is in compliance with the currently approved protocol/amendment(s), with GCP, and with applicable regulatory requirement(s).

A separate clinical monitoring plan (CMP) prepared by the CRO will describe:

- Person who will conduct the monitoring,
- Frequency monitoring will be done,
- Level of detail monitoring will be performed, and
- Distribution of monitoring reports.

10. STATISTICAL CONSIDERATIONS

10.1. Statistical Analysis Plan

The statistical analysis will be conducted following the principles as specified in the International Conference on Harmonization (ICH) Topic E9 (ICH, 1998). The final statistical analyses will be performed after database lock.

All data will be collected and verified prior to analysis. Detailed statistical procedures, listings, table shells, and figures will be provided in a statistical analysis plan (SAP) prior to analysis. The SAP will be finalized before study close-out and database lock. The following key statistical components and a detailed description will be documented in the SAP:

- Primary and secondary endpoints and how they will be measured
- Statistical methods and tests that will be used to analyze the endpoints
- Strategy that will be used if the statistical test assumptions are not satisfied
- Indication of whether the comparisons will be using one-tailed or two-tailed tests (with justification of the choice) and the level of significance to be used
- Identification of whether any adjustments to the significance level or the overall p value will be made to account for any planned or unplanned subgroup analyses or multiple testing
- Specification of potential adjusted analyses and a statement with which covariates or factors will be included
- Planned exploratory analyses and justification of their importance

The number of subjects enrolled, vaccinated, completed, or withdrawn will be summarized. Reasons for withdrawal, when known, will be provided. Demographic data will be summarized by descriptive statistics and will include total number of observations (n), mean, standard deviation (SD) and range for continuous variables, and number and percentages for dichotomous variables.

10.2. Statistical Hypotheses

The primary and secondary hypotheses will be assessed using Cox proportional hazards regression (time to first PCR-positive infection). These hypotheses tests will be supplemented with two-sided confidence intervals for the hazard ratios as described below.

The null (H_0) and alternative (H_1) hypotheses for the primary analysis of time to first malaria infection in Groups 1 and 4 is as follows:

H_0 : Among adults positive for *P. falciparum* at baseline the hazard rate for first malaria infection for RTS,S/AS01_E vaccinated adults (Group 1) is not different than that of adults administered the comparator rabies vaccine (Group 4) as measured by the hazard ratio.

H_1 : Among adults positive for *P. falciparum* at baseline the hazard rate for malaria infection for RTS,S/AS01_E vaccinated adults (Group 1) is different than that of adults administered the comparator rabies vaccine (Group 4) as measured by the hazard ratio.

The null and alternative hypotheses for the secondary efficacy analysis of time to first malaria infection in Groups 2 and 5 is as follows:

H_0 : Among adults negative for *P. falciparum* at baseline the hazard rate for malaria infection for RTS,S/AS01_E vaccinated adults (Group 2) is not different than that of adults administered the comparator rabies vaccine (Group 5) as measured by the hazard ratio.

H_1 : Among adults negative for *P. falciparum* at baseline the hazard rate for first malaria infection for RTS,S/AS01_E vaccinated adults (Group 2) is different than that of adults administered the comparator rabies vaccine (Group 5) as measured by the hazard ratio.

10.3. Analysis Datasets

10.3.1. Enrolled population

All subjects who provide written informed consent, regardless of the subject's screening, randomization and vaccination status in the study.

10.3.2. Total vaccinated cohort (TVC)

All subjects in the enrolled population who were randomized and received at least one vaccination.

10.3.3. Safety analysis population

All subjects in the TVC for which any safety data is available. All safety analyses will be performed using this population. The denominators for different safety endpoints may vary according to the number of subjects with available data for the specific endpoint.

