5.4. Participant Withdrawal or Termination

5.4.1. Reasons for Withdrawal or Termination

Subjects can leave the study at any time for any reason if they wish to do so without any penalty or loss of benefits to which they are otherwise entitled. Subjects can also be withdrawn from the study procedures at the discretion of the clinical investigator. The following reasons may lead to withdrawal of individual subjects:

- Withdrawal of informed consent by volunteer;
- Any serious adverse event;
- Any adverse event that, according to clinical judgment of the investigator, is considered as a definite contraindication to proceeding with the study procedures;
- Completely lost to follow-up (unable to contact after at least 3 phone or physical attempts by the study staff to locate the participant and 1 in-person attempt by a field supervisor to contact the individual; additional attempts may be made at the discretion of the PI);
- Pregnancy during immunization phase
- Ineligibility (arising during the study or retrospectively, having been overlooked at screening);
- If the investigator or DoD Research Monitor believes that continuation would be detrimental to the subject's well-being;
- Volunteer non-compliance with study requirements;
- Any other protocol deviation that results in a significant risk to the subject's safety.

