5.4.2. Handling of Participant withdrawals or termination

Investigators, or designee, will follow subjects who are withdrawn as result of a SAE/AE until resolution of the event and/or chronicity is established. Study staff will make an attempt to contact those subjects who do not return for scheduled visits or follow-up. Information relative to the withdrawal will be documented on the CRF. The investigator will document whether the decision to withdraw from the study was made by the subject or the investigator and which of the following possible reasons was responsible for withdrawal:

- serious adverse event
- non-serious adverse event
- protocol violation (specify)
- consent withdrawal, not due to an adverse event
- moved from the study area
- lost to follow-up

If a subject withdraws or is terminated from the study after enrolment and receipt of investigational product (including anti-malarial medications), including lost to follow-up, they will not be replaced. If a subject withdraws or is terminated from the study after enrolment but prior to receipt of investigational product, including lost to follow-up, (e.g., participant in group 3 who withdraws or is terminated between study visits 2 and 5) that participant may be replaced.

If the reason for withdrawal from the study is pregnancy during the immunization phase of the study, the participant will be withdrawn from any further immunizations, but will be followed for safety until delivery or termination of the pregnancy.

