8.3. Time Period and Frequency of Event Assessment and Follow-up

All solicited local and systemic AEs occurring within 7 days following administration of each dose of vaccine must be recorded on the CRF for the first 50 subjects in groups 1 and 2 and from all subjects in group 3 (Reactogenicity Cohort). All subjects being followed for solicited AEs will be offered a memory aid to assist in recall of AEs. All unsolicited AEs occurring within 28 days following administration of each dose of vaccine and, where applicable, course of per protocol scheduled anti-malarial treatment, must be recorded on the CRF for all subjects. All SAEs that occur will be collected and recorded from the time the subject consents to participate in the study until she/he is discharged. The occurrence of an AE or SAE may come to the attention of study personnel during study visits and field worker visits. Information to be collected includes event description, date of onset, clinician's assessment of severity, relationship to study product, and date of resolution/stabilization of the event. All AEs occurring while on study must be documented appropriately regardless of relationship. All AEs will be followed to adequate resolution.

Any medical condition that is present at the time that the participant is screened will be considered as baseline and not reported as an AE. However, if the study participant's condition deteriorates at any time during the study, it will be recorded as an AE.

After the initial AE/SAE report, the investigator is required to proactively follow each subject and provide further information per study reporting procedures (section 8.4). All AEs and SAEs documented at a previous visit/contact and designated as not recovered/not resolved or recovering/resolving will be followed-up.

Investigators will follow-up subjects:

- with SAEs or who are withdrawn from the study as a result of an AE, until the event has resolved, subsided, stabilized, disappeared, the event is otherwise explained, or the subject is lost to follow-up;
- or, in the case of other non-serious AEs, until the AE resolves, they complete the study, or they are lost to follow-up.

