10.4.4. Safety Analyses

For the safety analysis, data from all subjects from the safety analysis population will be included. All analyses will be descriptive. Data will be presented by dose, overall/dose and overall/subject. Results

will be summarized by study group. The percentage of subjects with at least one AE during the follow-up period will be tabulated with exact 95% CI (two-sided). No multiplicity adjustment will be implemented in analysis. The reports of solicited and unsolicited AEs will be reviewed by a physician and will be categorized by the MedDRA dictionary. The percentage of subjects with at least one report of unsolicited AE and reported up to 28 days after each anti-malarial course will be tabulated with exact 95% CI. The percentage of subjects with at least one report of unsolicited AE and reported up to 28 days after each vaccine dose will be tabulated with exact 95% CI.

The occurrence of SAEs will be determined on the safety analysis population. The proportion of subjects with an SAE, classified by the MedDRA preferred term level, reported from study start until study conclusion will be tabulated with exact 95% CI. Comparisons between groups will be done using Fisher's Exact Test for each preferred term. Serious adverse events (SAEs) occurring at any point during the trial will be summarized and relatedness to vaccine will be assessed.

Withdrawals due to AEs/SAEs will also be summarized. Vital signs which are outside of the normal range and clinically significant will also be listed in tables. The frequency of signs and symptoms will be compared between groups with the chi-square test or Fisher's exact test.

The occurrence of Grade 3 solicited and unsolicited general reactions will be determined on the Total Vaccinated Cohort. The proportion of subjects with a Grade 3 solicited and unsolicited reaction, reported from study start until study conclusion will be tabulated with exact 95% CI. Comparisons between groups will be done using Fisher's Exact Test.

The occurrence of adverse events will be determined on the Total Vaccinated Cohort. The proportion of subjects with an AE, classified by the MedDRA preferred term level, reported from study start until study conclusion will be tabulated with exact 95% CI. Comparisons between groups will be done using Fisher's Exact Test.

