APPENDIX B. EPOCH 1: TREATMENT AND IMMUNIZATION PHASE

Visit #	Treatment and Immunization Phase (Epoch 1)																
	2	3^	4^	5	6	7	8^	9^	10^	11	12 ¹	13	14^	15^	16^	17	18 ¹
Type of Visit (KC or FV) preferred	KC	FV	FV	KC	KC	KC	KC	FV	FV	KC	FV	KC	KC	FV	FV	KC	FV
Study day	-27	-26	-25	1	2	8	15	16	17	29	36	57	190	191	192	197	204
Permissible window (+/- days)*	2	0	0	3	0	+2	2	0	0	3	+2	3	2	0	0	3	+2
Issue subject's identification card	•																
Check inclusion/exclusion criteria	•			•			•			•			•				•
Record any intercurrent medical conditions	•			•			•			•			•				•
Record any concomitant medications/vaccinations	•			•	•	•	•	•		•		•	•				•
Record if subject belongs to reactogenicity sub-cohort ¹	•																
Check contraindications to vaccinations/anti-malarial medications	•			•			•			•			•				•
History of fever/Record body temperature	•			•			•			•			•				•
Focused/Symptom & physical exam as needed				•						•							•
DHA/piperaquine	•	•	•				•	•	•								
Primaquine (low dose)	•						•					•					
Coartem												•	•	•			
Record vital signs (BP, pulse, temperature)				•						•							•
Randomization upon completion of parasite PCR	•																
Vaccination				•						•							•
LABS																	
Complete blood count (Hb, WBC, PLT; 4 mL)				•													
Creatinine, ALT (4 mL)				•													
Hemoglobinopathy screen (4 mL)	•																
Urine Pregnancy test	•			•			•			•			•			•	
Buccal swab- HLA typing (Groups 1, 2, 3 only)	• ³																

Visit #	Treatment and Immunization Phase (Epoch 1)																
	2	3^	4^	5	6	7	8^	9^	10^	11	12 ¹	13	14^	15^	16^	17	18 ¹
Type of Visit (KC or FV) preferred	KC	FV	FV	KC	KC	KC	KC	FV	FV	KC	FV	KC	FV	FV	KC	FV	
Study day	-27	-26	-25	1	2	8	15	16	17	29	36	57	190	191	192	197	204
SAFETY DATA COLLECTION ¹																	
Record solicited local & systemic AEs				●	●	●				●	●					●	●
Record unsolicited AEs post anti-malarial treatment/ post vaccination	●	●	●	●	●	●	●	●	●	●	●	●	●	●	●	●	●
Record AEs/SAEs (fatal; AESI)	●	●	●	●	●	●	●	●	●	●	●	●	●	●	●	●	●
INVESTIGATIONAL ASSAYS																	
Blood serum sampling (10 ml) -refer to Appendix F for Group-specific timepoints ²	●			●						●		●				●	
CMI- PBMC from all RTS,S vaccinated subjects Groups 1,2,3 (30 mL)	●			●		●											
Whole blood transcriptomics all subjects (Paxgene; < 3 mL)	●			●	●	●											
PARASITEMIA ASSESSMENT																	
Blood sampling for PCR and DBS (0.35 to 0.5 ml)				●						●						●	

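### The adverse-event table for the first antimalarial course uses a vaccinated-only population, so subjects who take the drugs but never reach Dose 1 are left out

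*Protocol*

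**What the plan says.** Section 10.3.3 of the protocol defines the safety analysis population as "All subjects in the TVC for which any safety data is available" and adds: "All safety analyses will be performed using this population". Section 10.3.2 defines the TVC as "All subjects in the enrolled population who were randomized and received at least one vaccination". Section 10.4.4 repeats that safety analyses use the safety population. Among its tables is the percentage of subjects with at least one unsolicited AE "reported up to 28 days after each anti-malarial course will be tabulated with exact 95% CI".

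Appendix B places the first course of DHA/Pip with low-dose primaquine on days -27 to -25 and Dose 1 on day 1. Section 7.1.1 gives that course to Groups 1, 2, 4 and 5.

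The protocol foresees that some subjects will leave in between:

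- Section 5.4.1 lists as a reason for withdrawal "Any adverse event that, according to clinical judgment of the investigator, is considered as a definite contraindication to proceeding with the study procedures".
- Appendix B schedules "Check contraindications to vaccinations/anti-malarial medications" again at the Dose 1 visit.
- Section 5.4.2 says that for those who leave after "receipt of investigational product (including anti-malarial medications), including lost to follow-up, they will not be replaced".
- Section 8.3 requires that unsolicited AEs in the 28 days after a "course of per protocol scheduled anti-malarial treatment, must be recorded on the CRF for all subjects".

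**The concern.** The course-1 table is meant to describe what happens after a drug is taken, but entry to it depends on an event about four weeks later, namely vaccination. Almost the whole 28-day window closes before that event. A subject whose reaction to course 1 prevents Dose 1 is therefore always excluded, and such reactions are the most informative ones for tolerability of the antimalarial regimen.

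The same population rule reaches two other summaries in 10.4.4. The SAE table is described as running from study start, yet an SAE that ends participation before Dose 1 cannot appear in it. The summary of withdrawals due to AEs and SAEs has the same gap. SAEs that occur before Dose 1 in subjects who are later vaccinated are still counted.

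What is at stake is the accuracy of the aggregate antimalarial safety tables, not the protection of individual subjects.

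**Working it through.** **1. Who takes course 1.** The group sizes in 10.5.1 are 164, 128, 35, 164 and 128, which sum to the stated 619. Group 3 (35) takes no antimalarials, so 619 - 35 = 2 × 164 + 2 × 128 = 584 are planned to start course 1.

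**2. How much of the AE window precedes Dose 1.** Day -27 to day 1 is 27 days if there is no day 0 and 28 if there is. With visit windows of ±2 and ±3 days, the gap ranges from 22 to 33 days. So most or all of the 28-day window lies before a subject can qualify for the TVC.

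**3. Courses 2 and 3.** These start on days 15 and 190, after Dose 1, so those who take them after vaccination are already in the TVC. The problem is confined to course 1.

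**4. Whether other wording brings the subject back.**
- Section 10.3.3 lets denominators vary with data availability, but only among members of the safety population. It cannot admit someone outside the TVC.
- Section 10.4.6 mentions an exposed population. It is not defined and is used there for medical history.

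**5. Size.** The protocol gives only a 10% dropout for the whole study and nothing for the interval between course 1 and Dose 1, so the counts below are assumptions. Let *a* be the number with any AE after course 1 and *k* the number of those stopped before Dose 1. The true rate is *a*/584 and the table shows (*a* - *k*)/(584 - *k*).

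| *a* (true rate) | *k* = 1 | *k* = 3 | *k* = 6 | *k* = 12 |
|---|---|---|---|---|
| 29 (5.0%) | 28/583 = 4.8% | 26/581 = 4.5% | 23/578 = 4.0% | 17/572 = 3.0% |
| 58 (9.9%) | 57/583 = 9.8% | 55/581 = 9.5% | 52/578 = 9.0% | 46/572 = 8.0% |
| 117 (20.0%) | 116/583 = 19.9% | 114/581 = 19.6% | 111/578 = 19.2% | 105/572 = 18.4% |

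**6. Losses that are not caused by an AE.** If 12 AE-free subjects are lost and *a* = 58, the table shows 58/572 = 10.1% against a true 9.9%. If 1 of the 12 had an AE, it shows 57/572 = 10.0%. The net direction over all losses depends on the mix. The downward bias is certain only for the part due to AE-driven stops.

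**The case against.** The strongest reply is about reach. The safety objectives in section 3 and the endpoints in 4.2.2 concern the vaccine: SAEs, and AEs after each vaccination, with the SAE objective starting at Dose 1. A vaccinated-only population suits them. The antimalarial table is an additional descriptive one, for licensed products.

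Much of the information also survives elsewhere. Disposition summaries cover all subjects with reasons for discontinuation (10.4.5, 10.4.6), and the recorded reasons distinguish serious from non-serious AEs (5.4.2). SAEs are collected from consent (8.3) and reviewed by the research monitor (8.5.1). Possibly related DHA/Pip reactions go to the supplier within 24 hours (8.4.3).

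On size, the larger shifts need strong assumptions. Going from 9.9% to 8.0% requires 12 of the 58 subjects with any AE (21%) to be stopped, and going from 5.0% to 3.0% requires 12 of 29 (41%). Section 2.3.1.2 describes DHA/Pip reactions as generally mild. The exact 95% CI for 58/584 is 7.6% to 12.6%, and within a single group it is wider (16/164: 5.7% to 15.4%).

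These points limit the importance of the finding but do not remove it. Disposition reasons do not give AE terms or a rate with a confidence interval. Expedited reports are not a tabulation. Section 10.4.4 commits to an AE percentage after each course, and a percentage after a drug course should count those who took the drug. Nor is this a detail left open for the SAP, because the protocol fixes the population for every safety analysis.

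**Conclusion.** The concern holds. As written, 10.3.2, 10.3.3 and 10.4.4 together leave every subject who takes course 1 but is never vaccinated out of the course-1 AE table, and out of the population-based SAE and AE-withdrawal summaries. The reading rests on the protocol's own definitions and needs no assumption.

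The size does need assumptions and cannot be estimated from the documents. It is negligible if 0 or 1 subject is stopped because of an AE, and about 1 to 2 percentage points if 6 to 12 of 584 are. Courses 2 and 3, the vaccine safety tables and case-level safety oversight are essentially untouched. This should be fixed: the denominator is wrong for a table the plan promises, and correcting it is cheap.

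**What to change.** - Keep the TVC-based population for the vaccine safety tables. The vaccine SAE endpoint counted from Dose 1 can stay as it is.
- Add to 10.3 an antimalarial-exposed safety population: all randomised subjects who received at least one dose of study antimalarial.
- State in 10.4.4 that the AE tables by antimalarial course use this population, with those who started the given course as the denominator.
- List or tabulate separately, by AE term, the SAEs and AE withdrawals that occur after the first study product and before Dose 1, including those in never-vaccinated subjects.

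The cost is one added definition, one sentence and a listing. AEs are already recorded from Visit 2, so no new data or visits are needed. A protocol edit, even an administrative one, needs the ethics approvals set out in 13.2.2. The table shells and listings belong in the SAP under 10.1.
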